Appendix 4 CTCAE Term and Criteria for Classification*

CTCAE Term	Grade				
	Grade 1	Grade 2	Grade 3	Grade 4	Grade 5
Blood and lymphatic system disorders					
Anemia	10.0 g/dL \leq HGB < LLN	8.0 g/dL \leq HGB < 10.0 g/dL	HGB < 8.0 g/dL	---	---
Investigations					
Activated partial thromboplastin time prolonged	ULN < APTT \leq 1.5 \times ULN	1.5 \times ULN < APTT \leq 2.5 \times ULN	APTT > 2.5 \times ULN	---	---
Alanine aminotransferase increased	ULN < ALT \leq 3.0 \times ULN	3.0 \times ULN < ALT \leq 5.0 \times ULN	5.0 \times ULN < ALT \leq 20.0 \times ULN	ALT > 20.0 \times ULN	---
Alkaline phosphatase increased	ULN < ALP \leq 2.5 \times ULN	2.5 \times ULN < ALP \leq 5.0 \times ULN	5.0 \times ULN < ALP \leq 20.0 \times ULN	ALP > 20.0 \times ULN	---
Aspartate aminotransferase increased	ULN < AST \leq 3.0 \times ULN	3.0 \times ULN < AST \leq 5.0 \times ULN	5.0 \times ULN AST \leq 20.0 \times ULN	AST > 20.0 \times ULN	---
Blood bilirubin increased	ULN < T. Bil \leq 1.5 \times ULN	1.5 \times ULN < T. Bil \leq 3.0 \times ULN	3.0 \times ULN < T. Bil \leq 10.0 \times ULN	T. Bil > 10.0 \times ULN	---
Creatinine increased	BL < CREAT \leq 1.5 \times BL, or ULN < CREAT \leq 1.5 \times ULN	1.5 \times BL < CREAT \leq 3.0 \times BL, or 1.5 \times ULN < CREAT \leq 3.0 \times ULN	CREAT > 3.0 \times BL, or 3.0 \times ULN < CREAT \leq 6.0 \times ULN	CREAT > 6.0 \times ULN	---
GGT increased	ULN < γ -GTP \leq 2.5 \times ULN	2.5 \times ULN < γ -GTP \leq 5.0 \times ULN	5.0 \times ULN < γ -GTP \leq 20.0 \times ULN	γ -GTP > 20.0 \times ULN	---
Hemoglobin increased	In the case BL \leq ULN, ULN < HGB \leq ULN + 2 g/dL, In the case BL > ULN, BL < HGB \leq BL + 2 g/dL	In the case BL \leq ULN, ULN + 2 g/dL < HGB \leq ULN + 4 g/dL, In the case BL > ULN, BL + 2 g/dL < HGB \leq BL + 4 g/dL	In the case BL \leq ULN, HGB > ULN + 4 g/dL, In the case BL > ULN, HGB > BL + 4 g/dL	---	---
INR increased	ULN * < PT-INR \leq 1.5 \times ULN*	1.5 \times ULN* < PT-INR \leq 2.5 \times ULN*	PT-INR* > 2.5 \times ULN*	---	---
White blood cell decreased	3 \times 10 ³ / μ L \leq WBC < LLN	2 \times 10 ³ / μ L \leq WBC < 3 \times 10 ³ / μ L	1 \times 10 ³ / μ L \leq WBC < 2 \times 10 ³ / μ L	WBC < 1 \times 10 ³ / μ L	---

* Classification criteria are determined by reference to Common Terminology Criteria for Adverse Events (CTCAE) Version 4.0 [Published: May 28, 2009].

CTCAE Term	Grade				
	Grade 1	Grade 2	Grade 3	Grade 4	Grade 5
Metabolism and nutrition disorders					
Hypercalcemia	ULN < Ca ≤ 11.5 mg/dL	11.5 mg/dL < Ca ≤ 12.5 mg/dL	12.5 mg/dL < Ca ≤ 13.5 mg/dL	Ca > 13.5 mg/dL	---
Hyperkalemia	ULN < K ≤ 5.5 mEq/L	5.5 mEq/L < K ≤ 6.0 mEq/L	6.0 mEq/L < K ≤ 7.0 mEq/L	K > 7.0 mEq/L	---
Hypernatremia	ULN < Na ≤ 150 mEq/L	150 mEq/L < Na ≤ 155 mEq/L	155 mEq/L < Na ≤ 160 mEq/L	Na > 160 mEq/L	---
Hypoalbuminemia	3 g/dL ≤ ALB < LLN	2 g/dL ≤ ALB < 3 g/dL	ALB < 2 g/dL	---	---
Hypocalcemia	8.0 mg/dL ≤ Ca < LLN	7.0 mg/dL ≤ Ca < 8.0 mg/dL	6.0 mg/dL ≤ Ca < 7.0 mg/dL	Ca < 6.0 mg/dL	---
Hypokalemia	3.0 mEq/L ≤ K < LLN	3.0 mEq/L ≤ K < LLN	2.5 Eq/L ≤ K < 3.0 mEq/L	K < 2.5 mEq/L	---
Hyponatremia	130 mEq/L ≤ Na < LLN	---	120 mEq/L ≤ Na < 130 mEq/L	< 120 mEq/L	---

ALB = Albumin; APTT = Activated partial thromboplastin time; BL = Baseline value; CREAT = Creatinine; FIBRINO = Fibrinogen; HGB = Hemoglobin; LLN = Lower limit of normal range; PT-INR = International normalized ratio of prothrombin time; T.Bil = Total bilirubin; ULN = Upper limit of normal range

*: ULN for International normalized ratio of prothrombin time (PT-INR) is regarded as 1 if it will not be specified by the central laboratory.

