10.6 Laboratory Tests

For laboratory tests listed in [Table 4](#), summary statistics of observations and their changes from baseline will be calculated at each scheduled time point (Days 1, 8, 14, 35 and last observation) by treatment group.

Table 4 List of Laboratory Tests

Test	Items Evaluated
Haematology (except for platelet count)	Red blood cell count, white blood cell count, haemoglobin, and haematocrit
Blood Chemistry	Aspartate aminotransferase (AST), alanine aminotransferase (ALT), lactate dehydrogenase, gamma glutamyl transferase, alkaline phosphatase, total bilirubin, bilirubin direct, indirect bilirubin, total protein, albumin, blood urea nitrogen, serum creatinine, sodium, potassium, chloride, and calcium
Blood Coagulation/Fibrinolysis Assay	Prothrombin time-international normalized ratio (PT-INR), activated partial thromboplastin time

Individual clinically significant abnormalities (ICSA) will be summarized based on criteria which are determined by reference to Common Terminology Criteria for Adverse Events (CTCAE) Version 4.0 (see [Appendix 4](#)). For each CTCAE term shown in Appendix 4, the number and proportion of patients with a laboratory test result classified as grade 2 or more will be calculated at each scheduled time point (Days 1, 8, 14, 35) by treatment group. In addition, the number and proportion of patients with a laboratory test result classified as grade 2 or more at least once after the initiation of study drug will be calculated. For the term “hyponatremia”, the number and proportion of patients with a laboratory test result classified as grade 3 or more will be summarized because the term doesn’t have criteria for grade 2. The upper limit of normal range for PT-INR is regarded as 1 if it will not be specified by the central laboratory.

The number and proportion of patients who met the following criteria for liver function abnormalities will be calculated at each scheduled time point (Days 1, 8, 14, 35) by treatment group. The number and proportion of patients with liver function abnormalities after the initiation of study drug will also be calculated.

- AST or ALT $\geq 3 \times$ upper limit of normal (ULN) and total bilirubin $\geq 2 \times$ ULN
- AST or ALT $\geq 3 \times$ ULN and PT-INR ≥ 1.5
- AST/ALT ≥ 3

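### Hypokalaemia Grades 1 and 2 share one laboratory criterion in SAP Appendix 4, so the row for grade 2 or more in SAP 10.6 can give two different counts from the same data

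*SAP*

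**What the plan says.** Potassium is one of the blood chemistry tests in SAP Table 4 ("serum creatinine, sodium, potassium, chloride, and calcium"). SAP 10.6 then sets up a table of flagged results: "Individual clinically significant abnormalities (ICSA) will be summarized based on criteria which are determined by reference to Common Terminology Criteria for Adverse Events". One threshold serves every Appendix 4 term: "the number and proportion of patients with a laboratory test result classified as grade 2 or more will be calculated at each scheduled time point". A further count covers patients with such a result at least once after study drug was started.

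One term is exempted. Hyponatraemia is moved to a higher cut-off, with results "classified as grade 3 or more will be summarized because the term doesn’t have criteria for grade 2".

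In the hypokalaemia row of SAP Appendix 4, the Grade 1 cell and the Grade 2 cell both read "3.0 mEq/L ≤ K < LLN". Grade 3 is "2.5 Eq/L ≤ K < 3.0 mEq/L" and Grade 4 is any value under 2.5 mEq/L. No non-laboratory criterion is given that would separate Grade 1 from Grade 2.

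**The concern.** A threshold of grade 2 or more is meant to leave the mildest band out of the table. For hypokalaemia it cannot, because the mildest band is also printed as Grade 2. The SAP met a closely related problem for sodium, where there is no Grade 2 criterion, and dealt with it explicitly. Potassium has no distinct laboratory Grade 2 either, but was not given the same treatment.

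At stake is whether this row means what its label says. Protocol 7.8.9 separates an abnormal result (outside the reference range) from a clinically significant one (having a listed consequence, or so assessed by the investigator). For low potassium, the literal SAP rule makes the two the same. Two programmers working independently from this text could also produce different counts, each defensible.

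**Working it through.** The plan states no figure for this point, so there is nothing to reproduce first. The check is one of logic, followed by an illustration of size.

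**Inputs.** The four potassium bands are from SAP Appendix 4. The threshold, the hyponatraemia exception and the scheduled post-dose days (8, 14 and 35) are from SAP 10.6. The documents give no LLN for potassium, so 3.3, 3.5 and 3.6 mEq/L are assumed in turn.

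**Step 1: what the literal rule covers.** Grade 2 is [3.0, LLN), Grade 3 is [2.5, 3.0) and Grade 4 is below 2.5. Together they make up all K < LLN. Grade 1 is also [3.0, LLN), so no value is Grade 1 only. This holds for any LLN above 3.0.

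**Step 2: both readings on a grid.** Take potassium values from 2.0 mEq/L upward in steps of 0.1 and count those flagged as grade 2 or more.

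| Assumed LLN (mEq/L) | Grid values below LLN | Flagged if the higher grade applies | Flagged if the lower grade applies |
|---|---|---|---|
| 3.3 | 13 | 13 | 10 |
| 3.5 | 15 | 15 | 10 |
| 3.6 | 16 | 16 | 10 |

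The last column is K < 3.0 in each case, because Grade 2 is then empty. It is also what a cut-off of grade 3 or more would give. These are grid points that show which values change status; they are not expected patient frequencies.

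**Step 3: is there a tie rule?** SAP Table 3 orders categories by priority, but only for the severity and outcome of adverse events. Nothing equivalent exists for laboratory grades.

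**Step 4: comparison with neighbouring rows.** For hypocalcaemia, Grade 1 runs from 8.0 mg/dL to LLN and Grade 2 is "7.0 mg/dL ≤ Ca < 8.0 mg/dL", so a calcium just below normal is not counted. Anaemia, low white cell count and hypoalbuminaemia likewise place Grade 2 strictly below Grade 1. For sodium, the exception leaves out values from 130 mEq/L to LLN. Among the low-direction rows, only hypokalaemia lets the threshold reach up to LLN.

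**Step 5: illustrative size under the literal reading.** Assume LLN is the 2.5th percentile and a patient without any real change has all three post-dose samples.

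- Samples fully correlated: 1 − 0.975 = 2.5%.
- Samples independent: 1 − 0.975³ = 1 − 0.9269 = 7.3%.

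With 100 patients per arm, that is about 2.5 to 7.3 patients per arm. Any values below 3.0 mEq/L are included in these figures and would be counted under either reading, so the part in dispute is no larger than this.

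**The case against.** Four objections deserve an answer.

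First, Appendix 4 says its criteria were set by reference to a published grading standard, so the shared range may be a faithful numeric rendering and not a slip. The documents cannot settle this, and a reader should not infer a copying error. It does not rescue the row: the table is built from laboratory results alone, and Appendix 4 supplies nothing else to tell the grades apart.

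Second, the literal reading is not the only one. This stands in part. A value between 3.0 and LLN does meet the printed Grade 2 criterion, so the literal count is the more natural; but with no tie rule, the opposite handling is possible. The secure finding is an ambiguous count with a probable direction.

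Third, a reader might infer that trivial low values would bury the important ones, or that the row could not be set beside the others. The documents do not support either. SAP 10.6 also gives summary statistics of observed values and changes from baseline, SAP 6.1 provides patient listings, and under Protocol 7.7.7 and 7.8.9 the investigator assesses abnormal results and records clinically significant ones as adverse events. A marked fall would remain visible. The table compares arms within a term, no comparison across terms is planned, and hyponatraemia already uses a different cut-off.

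Fourth, the upper figure of 7.3% should not be read as a forecast. Independence of three samples from one patient within a few weeks is implausible, and a percentile from a healthy reference population need not hold in chronic liver disease. It is fair only as the top of a range.

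**Conclusion.** The point holds in a limited form. It is certain that hypokalaemia Grades 1 and 2 carry the same criterion and that SAP 10.6 exempts only hyponatraemia. It follows that the row counts either every patient with a potassium below LLN (literal reading) or only those below 3.0 mEq/L (lower grade taken), and that the SAP does not choose between them. This requires only that LLN exceeds 3.0 mEq/L.

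The consequence is small. It concerns one descriptive safety row, graded alike in both arms, and potassium is not among the stated adverse events of special interest. No hypothesis test, alpha, sample size or efficacy result depends on it. A reader might infer a bias between arms or a distorted safety conclusion; nothing in the documents supports that. The 2.5% to 7.3% range rests on an assumed LLN percentile and complete sampling, and the finding does not depend on it.

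**What to change.** Choose one of two changes:

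- In SAP 10.6, extend the hyponatraemia exception to hypokalaemia, tabulating grade 3 or more, and give as the reason that laboratory data alone do not separate Grade 2 from Grade 1.
- In SAP Appendix 4, give hypokalaemia Grade 2 a laboratory range distinct from Grade 1, and leave 10.6 as it is.

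A tie rule by itself would make the count reproducible but would not restore a usable Grade 2: taking the higher grade empties Grade 1, and taking the lower empties Grade 2.

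The cost is one line of SAP text and one programming condition. The first option has a small downside: values from 3.0 mEq/L up to LLN leave this row, though they stay in the summary statistics and listings. While the row is open, check the unit at the lower bound of the Grade 3 cell, which reads Eq/L where the rest of the row has mEq/L.
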